4. DRUGS THAT MAY PROLONG QT INTERVAL

The drugs listed in this section are taken from information provided by The Arizona Center for Education and Research on Therapeutics and The Critical Path Institute, Tucson, Arizona and Rockville, Maryland. Ref: http://www.arizonacert.org/medical-pros/drug-lists/drug-lists.htm.

4.1 Drugs known to prolong QT interval

The following drugs are known to prolong QT interval or induce Torsades de Pointes and should not be combined with AZD9291. Recommended withdrawal periods following cessation of treatment with these agents are provided in the table.

Table 4Drugs prolonging QT interval

Contraindicated drug	Withdrawal period prior to AZD9291 start
Clarithromycin, droperidol, erythromycin, procainamide	2 days
Cisapride, disopyramide, dofetilide, domperidone, ibutilide, quinidine, sotalol, sparfloxacin, thioridazine	7 days
Bepridil, chlorpromazine, halofantrine, haloperidol, mesoridazine	14 days
Levomethadyl, methadone, pimozide	4 weeks
Arsenic trioxide	6 weeks*
Pentamidine	8 weeks
Amiodarone, chloroquine	1 year

* Estimated value as pharmacokinetics of arsenic trioxide has not been studied

4.2 Drugs that may possibly prolong QT interval

The use of the following drugs is permitted (notwithstanding other exclusions and restrictions) provided the patient has been stable on therapy for the periods indicated.

Drug	Minimum treatment period on medication prior to AZD9291 start
Alfuzosin, chloral hydrate, ciprofloxacin, dolasetron, foscarnet, galantamine, gemifloxacin, isridipine, ketoconazole, levofloxacin, mexiletine, nicardipine, octreotide, ofloxacin, ondansetron, quetiapine, ranolazine, telithromycin, tizanidine, vardenafil, venlafaxine, ziprasidone	2 days
Amantadine, amitriptyline, amoxapine, clozapine, doxepin, felbamate, flecainide, fluconazole, fosphenytoin, gatifloxacin, granisetron, imipramine, indapamide, lithium, moexipril/HCTZ, moxifloxacin, risperidone, roxithromycin, sertraline, trimethoprin-sulfa, trimipramine, voriconazole	7 days
Azithromycin, citalopram, clomipramine, itraconazole, nortriptyline, paroxetine, solifenacin, tacrolimus	14 days
Fluoxetine	5 weeks
Protriptyline	6 weeks
Tamoxifen	8weeks

Table 5Drugs that may prolong QT interval

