4.3.1 Concomitant treatments

Information on any treatment in the 4 weeks prior to starting study treatment and all concomitant treatments given during the study, with reasons for the treatment, will be recorded in the Case Report Form (CRF). After permanent discontinuation of AZD9291 and 28 day follow up, only subsequent regimens of anti-cancer therapy will be recorded in CRF. If medically feasible, patients taking regular medication, with the exception of potent inhibitors or inducers of CYP3A4 and inhibitors of CYP2C8 (see Section 4.2 exclusion 1, and Appendix H), should be maintained on it throughout the study period. Patients taking concomitant medications whose disposition is dependent upon intestinal CYP3A4 and/or transporter proteins and/or CYP2C8 and

which have a narrow therapeutic index should be closely monitored for signs of changed tolerability as a result of increased exposure of the concomitant medication whilst receiving AZD9291. Guidance on medications that require close monitoring is given in Appendix H.

Other anticancer agents, investigational agents and radiotherapy should not be given while the patient is on study treatment.

Pre-medication will be allowed after, but not before the first dose of study treatment. This includes management of diarrhoea, nausea and vomiting.

Blood transfusions are allowed at any time during the study.

Granulocyte colony stimulating factors should not be used prophylactically during Cycle 1. Use of prophylactic colony stimulating factors may be considered after Cycle 1 following discussion with the AstraZeneca Study Team Physician.

Patients may receive treatment with corticosteroids and/or bisphosphonates for the treatment of bone metastases. Patients may also receive radiotherapy for painful bony metastases.

Supportive care and other medications that are considered necessary for the patient's well-being, may be given at the discretion of the investigator.

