Appendix H Guidance regarding Potential Interactions With Concomitant Medications

TABLE OF CONTENTS

PAGE

	TABLE OF CONTENTS	.2
1.	DRUGS INHIBITING CYP3A4 OR CYP2C8 METABOLISM THAT ASTRAZENECA STRONGLY RECOMMEND ARE NOT COMBINED WITH AZD9291	3
2.	DRUGS INDUCING CYP3A4 METABOLISM THAT ASTRAZENECA STRONGLY RECOMMEND ARE NOT COMBINED WITH AZD9291	.4
3.	MEDICINES WHOSE EXPOSURES MAY BE AFFECTED BY AZD9291 THAT ASTRAZENECA CONSIDERS MAY BE ALLOWED WITH CAUTION	.4
4.	DRUGS THAT MAY PROLONG QT INTERVAL	.5
4.1	Drugs known to prolong QT interval	.5
4.2	Drugs that may possibly prolong QT interval	.5

LIST OF TABLES

Table 1	Drugs inhibiting CYP3A4 or CYP2C8	.3
Table 2	Drugs inducing CYP3A4	.4
Table 3	Exposure, pharmacological action and toxicity may be increased by AZD9291	.4
Table 4	Drugs prolonging QT interval	.5
Table 5	Drugs that may prolong QT interval	.6

GUIDANCE REGARDING POTENTIAL INTERACTIONS WITH CONCOMITANT MEDICATIONS

The use of any natural/herbal products or other "folk remedies" should be discouraged, but use of these products, as well as use of all vitamins, nutritional supplements, and all other concomitant medications must be recorded in the eCRF.

AZD9291 is an investigational drug for which no data on in vivo interactions are currently available. Based on in vitro data and predicted clinical exposure data, AZD9291 is considered unlikely to cause clinically significant drug interactions through inhibition or induction of cytochrome P450 enzyme activity. In vitro data have shown that the principal CYP enzymes responsible for the Phase I metabolism of AZD9291 are CYP2C8 and CYP 3A4.

1. DRUGS INHIBITING CYP3A4 OR CYP2C8 METABOLISM THAT ASTRAZENECA STRONGLY RECOMMEND ARE NOT COMBINED WITH AZD9291

The contribution of Phase I metabolism to the total clearance of AZD9291 is currently unknown but, to ensure patient safety, the following potent inhibitors of CYP2C8 and CYP3A4 must not be used during this study for any patient receiving AZD9291.

Table 1Drugs inhibiting CYP3A4 or CYP2C8

Contraindicated drugs	Withdrawal period prior to AZD9291 start
Clarithromycin, telithromycin, troleandomycin	1 week
Gemfibrozil	
Indinavir, lopinavir, nelfinavir, ritonavir, saquinavir, tipranavir, telaprevir	
Itraconazole, ketoconazole, posaconazole, voriconazole	
Mibefradil	
Nefadozone	

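### Appendix H Table 5 lists as permitted at entry four potent CYP inhibitors that Table 1 of the same appendix forbids

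*Protocol*

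**What the plan says.** Appendix H of the protocol gives two kinds of drug guidance.

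Section 1 concerns metabolism. It says that "the following potent inhibitors of CYP2C8 and CYP3A4 must not be used during this study for any patient receiving AZD9291", and gives patient safety as the reason. Table 1 then names the drugs. Two of its rows are "Itraconazole, ketoconazole, posaconazole, voriconazole" and "Clarithromycin, telithromycin, troleandomycin". The withdrawal period printed for the table is 1 week.

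Section 4 concerns QT prolongation and draws its lists from outside the trial ("The drugs listed in this section are taken from information provided by" two external organisations). Its Section 4.2 opens with "The use of the following drugs is permitted (notwithstanding other exclusions and restrictions" and makes the permission depend on the patient being stable on the drug. The column in Table 5 is headed "Minimum treatment period on medication prior to AZD9291 start".

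The protocol body bears on both. Section 4.2, exclusion criterion 1, bars patients who are taking potent CYP3A4 or CYP2C8 inhibitors or cannot stop them at least 1 week before the first dose, and it refers to Appendix H. Section 4.3.1 asks that regular medication be continued, "with the exception of potent inhibitors or inducers of CYP3A4 and inhibitors of CYP2C8 (see Section 4.2 exclusion 1, and Appendix H"). Section 4.3, item 3, is softer: patients are to try to avoid such drugs where feasible, and may receive whatever is clinically indicated to treat an adverse event. Section 5.3.2, under cardiovascular effects, sends sites to Appendix H for drugs that may prolong QT.

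**The concern.** Some drugs appear in both tables, and the two tables ask for opposite things before AZD9291 starts. Table 1 asks for time off the drug. Table 5 asks for time on it. The word *notwithstanding* normally means in spite of, so on its face the Table 5 permission prevails over the Table 1 ban and over exclusion criterion 1.

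The risk is practical. A site that checks a patient's antifungal or antibiotic against the QT lists, as Section 5.3.2 directs, finds it marked as permitted and may leave the patient on it at entry. Section 2.3 names CYP3A4, and to a lesser extent CYP2C8, as the principal P450 enzymes metabolising AZD9291, and reports some evidence of QT increase in animals. Section 5.1.3 counts confirmed QTc prolongation as dose-limiting. The four shared drugs are, by the appendix's own lists, both potent inhibitors and possible QT prolongers. Pharmacokinetics is also a secondary objective.

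**Working it through.** No figure in the plan is involved, so the check is a comparison of lists.

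**Step 1: find the overlap.** Table 1 names 17 drugs. Table 5 names 22 in the 2-day row, 22 in the 7-day row, 8 in the 14-day row and 3 in the longer rows, so 22 + 22 + 8 + 3 = 55. Exactly four names are common to both.

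| Drug | Table 1 | Table 5 |
|---|---|---|
| Ketoconazole | must not be used; 1 week off | permitted if stable for 2 days |
| Telithromycin | must not be used; 1 week off | permitted if stable for 2 days |
| Voriconazole | must not be used; 1 week off | permitted if stable for 7 days |
| Itraconazole | must not be used; 1 week off | permitted if stable for 14 days |

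The 1-week period is printed once in Table 1. I take it to apply to every row, which agrees with the 1 week in exclusion criterion 1.

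**Step 2: compare the timing.** Take the Table 5 period to run up to the start of AZD9291. A patient relying on it is then on the drug during the 7 days in which Table 1 and exclusion criterion 1 require the patient to be off it: for at least 2 of those days with ketoconazole or telithromycin, and for all 7 with voriconazole or itraconazole. The conflict continues after the first dose, because Table 1 also bars use during the study.

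**Step 3: try each reading of the parenthesis.**
- *In spite of all other restrictions* (the literal sense): Table 5 allows four drugs that Table 1 and exclusion criterion 1 forbid. The appendix contradicts itself.
- *Subject to other restrictions*: Table 1 governs. The four entries can never be used, yet they stand under a statement of permission.
- *In spite of QT restrictions only* (such as exclusion criterion 5): the CYP ban is untouched and the result is the same as on the second reading.

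**Step 4: look for text that reconciles the tables.** The softer wording of Section 4.3, item 3, does not permit entry on these drugs: it asks for avoidance, requires discontinuation before screening, and makes its allowance for treating adverse events. The continuation rule in Section 4.3.1 carves potent inhibitors out. The amendment at the end of the document revises Table 1, keeps all four drugs in it, and shows no change to Table 5. Nothing states which table takes precedence.

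**The case against.** The strongest reply is that Section 4 is a QT list from a QT source and Section 1 is a CYP list, so each should be read within its own subject. On that view Table 1 governs and the four entries are merely redundant. A reader might infer that the tables contradict each other on any reading. The documents do not support that: the contradiction depends on the literal sense of one word. What survives is that the literal sense is the one a site will read, and that on the other readings a banned drug is still listed as permitted.

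A second reply is that entry is already controlled, and this largely stands. Exclusion criterion 1 covers these patients, Sections 4 and 5.4.2 allow no exceptions to eligibility, and Appendix H invites queries to the sponsor. To act on Table 5, a site must overlook several other instructions. Nor is it right that the two tables cannot both be obeyed. Table 5 permits and does not require, so a patient who stops a week before dosing breaches neither.

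Third, the ban is less uniform than Table 1 alone suggests. The heading of Appendix H Section 1 is phrased as a strong recommendation, and Section 4.3, item 3, is softer still. This tempers the account of the ban but does not support Table 5.

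A reader might also add clarithromycin, which is in Table 1 with 1 week and in Table 4 ("Clarithromycin, droperidol, erythromycin, procainamide") with 2 days. That is not a further contradiction: both tables prohibit it, and observing the longer period satisfies both.

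**Conclusion.** The point stands for four drugs: ketoconazole, telithromycin, voriconazole and itraconazole. Read as written, Table 5 permits what Table 1 and exclusion criterion 1 forbid. Read charitably, it lists drugs that can never be used under it. Either way the entries should go.

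Severity is low to moderate. The consequence is a possible safety and exposure problem in any patient kept on one of these drugs at entry. Its size cannot be estimated: the protocol gives no data on how many patients take them, and Appendix H says the contribution of Phase I metabolism to AZD9291 clearance is unknown. It would be tempting to infer a material effect on the trial's results, but nothing in the document supports that. Sample size, precision statements and the primary analysis are unchanged.

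The conclusion rests on two assumptions: that the 1-week period covers all rows of Table 1, and that the Table 5 period ends at the start of AZD9291. The conflict over use during the study needs neither.

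**What to change.** Delete ketoconazole, telithromycin, voriconazole and itraconazole from Table 5. Add one sentence to Appendix H: the CYP prohibitions and withdrawal periods in Tables 1 and 2 apply regardless of Tables 4 and 5, and where two withdrawal periods are given the longer one applies. The last clause also settles clarithromycin at 1 week.

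Do not replace *notwithstanding* with a blanket *subject to*. If the word was meant to lift the QT restrictions, that change could put the other 55 − 4 = 51 drugs in Table 5 back under exclusion criterion 5 and undo a permission the sponsor intended. If the word is edited at all, limit the edit to the CYP restrictions.

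The cost is a wording change with no effect on data collection or analysis. It would have to be carried in a protocol amendment: the sponsor has already used one to revise Appendix H, and Appendix D Section 1.4 calls for ethics committee approval of amendments before they are implemented. It could travel with the next one.

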Appendix I Patient Reported Outcomes (LC13)

Patients sometimes report that they have the following symptoms or problems. Please indicate the extent to which you have experienced these symptoms or problems during the past week. Please answer by circling the number that best applies to you.

Du	ring the past week :	Not at	A	Quite	Very
		All	Little	a Bit	Much
31.	How much did you cough?	1	2	3	4
32.	Did you cough up blood?	1	2	3	4
33.	Were you short of breath when you rested?	1	2	3	4
34.	Were you short of breath when you walked?	1	2	3	4
35.	Were you short of breath when you climbed stairs?	1	2	3	4
36.	Have you had a sore mouth or tongue?	1	2	3	4
37.	Have you had trouble swallowing?	1	2	3	4
38.	Have you had tingling hands or feet?	1	2	3	4
39.	Have you had hair loss?	1	2	3	4
40.	Have you had pain in your chest?	1	2	3	4
41.	Have you had pain in your arm or shoulder?	1	2	3	4
42.	Have you had pain in other parts of your body?	1	2	3	4
	If yes, where				
43.	Did you take any medicine for pain?				
	1 No 2 Yes				
	If yes, how much did it help?	1	2	3	4

© QLQ-C30-LC13 Copyright 1994 EORTC Quality of life Group. All rights reserved

Clinical Study Protocol	Appendix J
Drug Substance	AZD9291
Study Code	D5160C00001
Edition Number	1
Date	

Appendix J Patient Reported Outcomes (QLQ-C30)

EORTC QLQ-C30 (version 3)

We are interested in some things a bout you and your health. Please a nswer all of the questions your self by circling the number that best applies to you. There are no "right" or "wrong" answers. The information that you provide will remain strictly confidential.

Yo	ase fill in your initials: ur birthdate (Day, Month, Year): day's date (Day, Month, Year): 31				
1.	Do you have any trouble doing strenuous activities,	Not at All	A Little	Quite a Bit	Very Much
1.	like carrying a heavy shopping bag or a suitcase?	1	2	3	4
2.	Do you have any trouble taking a long walk?	12	3		4
3.	Do you have any trouble taking a short walk outside of the house?	1	2	3	4
4.	Do you need to stay in bed or a chair during the day?	1	2	3	4
5.	Do you need help with eating, dressing, washing yourself or using the toilet?	1	2	3	4
Dı	uring the past week: N	ot at All	A Little	Quite a Bit	Very Much
6.	Were you limited in doing either your work or other daily activities?) 1	2	3	4
7.	Were you limited in pursuing your hobbies or other leisure time activities?	1	2	3	4
8.	Were you short of breath?	1	2)	3	4
9.	Have you had pain?	I	2	3	4
10.	Did you need to rest?		2	3	4
11.	Have you had trouble sleeping?	1	2	3	4
12.	Have you felt weak?	1	2	3	4
13.	Have you lacked appetite?	1	2	3	4
14.	Have you felt nauseated?	1	2	3	4
15.	Have you vomited?	12	3		4
16.	Have you been constipated?	1	2	3	4

Please go on to the next page

Du	ring the past week:	Not at All	A Little	Quite a Bit	Very Much
17.	Have you had diarrhea?	1	2	3	4
18.	Were you tired?	12	3		4
19.	Did pain interfere with your daily activities?	1	2	3	4
20.	Have you had difficulty in concentrating on things, like reading a newspaper or watching television?	1	2	3	4
	Did you feel tense?	1	2	3	4
	Did you worry? Did you feel irritable?	1 1	2 2	3 3	4
24.	Did you feel depressed?	1	2	3	4
25.	Have you had difficulty remembering things?	1	2	3	4
26.	Has your physical condition or medical treatment interfered with your family life?	1 2	3		4
27.	Has your physical condition or medical treatment interfered with your social activities?	1 2	3		4
28.	Has your physical condition or medical treatment caused you financial difficulties?		2	3	4
		iber b etwe	en 1 ai	nd 7 th	a t
bes	t applies to you				
29.	How would you rate your overall health during the past week?				
	1234 56	7			
Ver	y poor	Excellent			

4.3 Restrictions

Previous text:

1. Females of child-bearing potential should use reliable methods of contraception from the time of screening until 3 months after discontinuing study treatment. Acceptable methods of contraception include abstinence, tubal ligation, oral or transdermal contraceptives, copperbanded intra-uterine devices and vasectomised partner. All hormonal methods of contraception should be used in combination with the use of a condom by their male sexual partner for intercourse.

Revised text:

1. Females of child-bearing potential should use reliable methods of contraception from the time of screening until 3 months after discontinuing study treatment. Acceptable methods of contraception include **total sexual** abstinence, tubal ligation, **hormonal contraceptives that are not prone to drug-drug interactions (IUS Levonorgestrel Intra Uterine System (Mirena), Medroxyprogesterone injections (Depo-Provera)**), copper-banded intra-uterine devices and vasectomised partner. All hormonal methods of contraception should be used in combination with the use of a condom by their male sexual partner for intercourse.

Section of protocol affected:

4.3.1 Concomitant treatments

Previous text:

Information on any treatment in the 4 weeks prior to starting study treatment and all concomitant treatments given during the study, with reasons for the treatment, will be recorded in the Case Report Form (CRF). After permanent discontinuation of AZD9291 and 28 day follow up, only subsequent regimens of anti-cancer therapy will be recorded in CRF. If medically feasible, patients taking regular medication, with the exception of potent inhibitors or inducers of CYP3A4 and inhibitors of CYP2C8 (see Section 4.2 exclusion 1, and Appendix H), should be maintained on it throughout the study period. Patients taking concomitant medications whose disposition is dependent upon intestinal CYP3A4 and/or transporter proteins and/or CYP2C8 and which have a narrow therapeutic index should be closely monitored for signs of changed tolerability as a result of increased exposure of the concomitant medication whilst receiving AZD9291. Guidance on medications that require close monitoring is given in Appendix H.

Revised text:

Information on any treatment in the 4 weeks prior to starting study treatment and all concomitant treatments given during the study, with reasons for the treatment, will be recorded in the Case Report Form (CRF). After permanent discontinuation of AZD9291 and 28 day follow up, only subsequent regimens of anti-cancer therapy will be recorded in CRF. If medically feasible, patients taking regular medication, with the exception of potent inhibitors or inducers of CYP3A4 and inhibitors of CYP2C8 (see Section 4.2 exclusion 1, and Appendix H), should be maintained on it throughout the study period. Patients taking concomitant medications whose disposition is dependent upon CYP3A4, CYP2C8 or **BCRP** and which have a narrow therapeutic index should be closely monitored for signs of changed tolerability as a result of increased exposure of the concomitant medication whilst receiving AZD9291. **Patients taking concomitant medications whose disposition is dependent upon CYP3A4, CYP1A2, CYP2C or p-glycoprotein and which have a narrow therapeutic index should be closely monitored for signs of changed tolerability as a result of increased exposure of the concomitant medication whilst receiving AZD9291. Patients taking concomitant medications whose disposition is dependent upon CYP3A4, CYP1A2, CYP2C or p-glycoprotein and which have a narrow therapeutic index should be closely monitored for reduction in therapeutic activity as a result of the reduced exposure of the concomitant medication whilst receiving AZD9291. Guidance on medications that require close monitoring is given in Appendix H.**

Up to 3 fold increase in exposure may occur in statin exposure when coadministered with AZD9291. It is recommended that the starting and maintenance dose of statins should be as low as possible and should be guided by the statin label. Monitoring of low-density lipoprotein (LDL) cholesterol levels is advised. If the patient experiences any potentially relevant adverse events suggestive of muscle toxicity including unexplained muscle pain, tenderness, or weakness, particularly if accompanied by malaise or fever, the statin should be stopped, creatine kinase (CK) levels should be checked, and any appropriate further management should be taken.

Patients taking warfarin should be monitored regularly for changes in prothrombin time or INR.

Section of protocol affected:

6.5.2 Administration of PROs

Previous text:

Questionnaires will be administered using paper questionnaires. The patient should complete the questionnaires at the scheduled clinic visit at screening, and every 6 weeks relative to the first dose of multiple dosing, discontinuation and progression as specified in the study plan (Table 2, Table 3 and Table 4). The patient should also complete a questionnaire progression. If any scheduled PRO assessment is not completed the reason for non-completion should be recorded.

Revised text:

Questionnaires will be administered using paper questionnaires. The patient should complete the questionnaires at the scheduled clinic visit at screening, **baseline** (cycle 1 day 1) and every 6 weeks relative to the first dose of multiple dosing, discontinuation and progression as specified in the study plan (Table 2, Table 3 and Table 4) The patient should also complete a questionnaire progression. If any scheduled PRO assessment is not completed the reason for non-completion should be recorded.

